6.3.10. Nutritional Assessment

At the initial visit, the registered dietitian will conduct a complete review of the subject's caloric intake, and work with PI to determine the optimal amount of oil based on the age, current caloric intake and dosing determined in Protocol 1. Additional nutritional counseling will be provided, including instructions on limiting other fats and simple sugars

in the subject's diet to minimize the risk of weight gain. The initial consult will take approximately 60 minutes.

During each monthly phone call, the registered dietitian will evaluate the subject's current dietary intake to determine if any changes in amount of C7 administered are necessary. As these are primarily growing children, it is important to evaluate caloric intake regularly, as these needs can change dramatically over even a few months if the child goes through a growth spurt. Any changes in caloric intake, up or down, will be accounted for, and PI will be consulted if the changes are great enough to warrant a change in amount of daily C7 administration. This procedure will take approximately 20 minutes.

6.3.11. Seizure count

For one month prior to each study visit and for each month of participation, parents and caregivers will be asked to track how many observable seizures their child has. Although we have evidence that many patients with G1D have frequent abnormal EEG without observable seizures, seizure count is considered a gold standard in epilepsy research and will be included as a secondary measure.

6.3.12. Electroencephalogram

EEG recordings will be performed with standard 10-20 electrode recording placement and recorded by digital devices with a 1000 Hz sampling rate. Recordings will last for 8 hours during daytime to provide a broad sample of the awake state. The recordings will be stored electronically and locally until they are ready for central review. Prior to transmission for central review the tracings will be de-identified and assigned a unique study number so that the EEG interpretation can be conducted in a blinded fashion. Central EEG review will be done by [name].

Central EEG readings will be done using an FDA-approved specialized software designed for interpreting recordings from a wide variety of manufacturers (Insight by Persyst). This will permit uniform interpretation of the tracings and will also allow for precise quantitative analysis of the spike-wave discharges. The study will be pruned so that only awake portions are present before the analyses begin and the total duration of the awake recording will be noted.

There will be three measures of the cerebral electrical activity. The first will be a determination of the frequency of the posterior dominant rhythm. This will be measured bilaterally in a non-drowsy portion of the awake recording after eye closure.

The second measure will be the total number of generalized spike-wave discharges will be counted in the awake state only. Computerized automated spike detection will be run on the sample and then the resultant spikes will be analyzed using the spike clustering feature of Insight. This will allow the central reader to reject all detections that are not generalized spikes, and the resultant number of bona fide generalized spikes will be displayed. The ratio of generalized spike-wave discharges per unit time of the awake tracing will be recorded.

The final and third analysis will be of the total number of generalized 3 Hz spike-wave discharges lasting longer than 3 seconds. Here, the rhythmic burst detection system of Insight will be used to identify every burst, and these will be reviewed by the central reader to ensure that they are all accurate detections of the specified time duration. The total number will be recorded and once again compared to the total duration of the awake tracing.

Laboratory Evaluations

Hematological and chemical profiles (including blood cell count, comprehensive metabolic panel, lactate, lipid panel, urine and or blood pregnancy test if appropriate, and beta-hydroxybutyric acid (a ketone body generated by ketogenic diets) will be measured by standard clinical laboratory methods and compared to normal values established in each laboratory. Measurement of C7 ketones will be conducted by a collaborating research laboratory.

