4.3.4. Group Assignment

This is an open-label study; there is no group assignment.

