10. DATA COLLECTION, SITE MONITORING, AND ADVERSE EXPERIENCE REPORTING

10.1. Records to Be Kept

All signed informed consent forms will be maintained in a locked filing cabinet accessible only to the [name], Clinical Director, and research coordinator. This cabinet is located in a limited-access room which requires an authorized badge to enter.

All records collected for research-only purposes (research EEG, metabolic assays) will be maintained in a secure fashion. Paper records will be maintained in a locked filing cabinet in a limited-access room. Electronic records will be maintained on an internal, secure UTSW server accessible only by authorized username and password. These servers are backed up nightly, are HIPAA and HiTECH compliant, and are behind the same level of security as UT Southwestern and Children's Medical Center Dallas' medical records.

Subject's will be assigned a study ID, and all materials collected for research purposes will be de-identified using this study ID, including data and case report forms. A file containing the link will be maintained for the duration of active study procedures and during data cleaning. Once the data has been cleaned, the file containing the link to patient ID will be deleted and destroyed.

Records collected for clinical and research purposes (e.g., blood tests completed at Children's Medical Center, and neurological evaluations done at each visit) will become part of the subject's medical record at Children's Medical Center and may be copied and transferred to the subject's primary referring physician at the patient request.

Neuropsychological test forms are not part of the medical records. Results from these tests will become part of the subject's research record, but source documents will be maintained by the Department of Psychology at Children's Medical Center in accordance with internal privacy laws, and are subject to a greater level of confidentiality than the primary medical record.

The investigator-sponsor will maintain records in accordance with Good Clinical Practice guidelines; to include:

- FDA correspondence related to the IND application and Investigational Plan; including copies of submitted Form FDA 3500 A, supplemental IND applications, current investigator lists, progress reports, and failure to obtain informed consent reports;

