11.2. Subject Confidentiality

All laboratory specimens, evaluation forms, reports, video recordings, and other records that leave the site will be identified only by the Study Identification Number (SID) to maintain subject confidentiality. All records will be kept in a locked file cabinet. All computer entry and networking programs will be done using SIDs only. Clinical information will not be released without written permission of the subject, except as necessary for monitoring by IRB, the FDA, the NINDS, the OHRP, the sponsor, or the sponsor's designee.

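### The blinding described for the central EEG reading does not assure that the reader is masked to visit and oil state, the contrast on which the EEG treatment effect rests

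*Combined protocol and SAP*

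**What the plan says.** Section 6.3.12 (Electroencephalogram) sends the tracings to one central reader and states that "the tracings will be de-identified and assigned a unique study number so that the EEG interpretation can be conducted in a blinded fashion". No other masking step is described there or elsewhere.

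The reader's work is partly judgement. For the spike-wave count, automated detection and clustering come first: "This will allow the central reader to reject all detections that are not generalized spikes". For bursts longer than 3 seconds, software identifies candidates and "these will be reviewed by the central reader to ensure that they are all accurate detections of the specified time duration". The posterior dominant rhythm is measured in a non-drowsy awake portion after eye closure, with no automated step described.

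On the design, Section 4.3.4 states: "This is an open-label study; there is no group assignment". Section 1.2 defines the EEG benefit as a change from the pre-C7 baseline, both acutely and over 6 months. Section 9.5 analyses EEG over time by GEE.

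On codes, Section 10.1 says that each subject gets a study ID and that "all materials collected for research purposes will be de-identified using this study ID, including data and case report forms". Section 11.2 says that records leaving the site "will be identified only by the Study Identification Number (SID) to maintain subject confidentiality".

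**The concern.** Blinding protects an outcome only if it hides the condition being compared. Every subject receives C7, so for the EEG treatment effect that condition is time relative to oil: before, on, or after. Concealing who the patient is does not by itself conceal this. A reader who knows that a tracing is on oil, and expects fewer discharges, may reject borderline detections more readily, and the count falls with no drug effect.

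EEG is the only outcome for which the protocol claims blinded interpretation. Study physicians rate the ataxia and global impression scales (6.3.5, 6.3.6), and caregivers complete the behaviour scales (6.3.9), all in an open-label trial. Section 9.1 treats EEG as a surrogate marker to be related to attention scores, and the remaining outcomes enter the go/no-go decision when the attention response is intermediate (51–79%). If the EEG is to carry more weight because it was read blind, the blinding should cover the contrast being tested.

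**Working it through.** The plan gives no figure for reader error, EEG variability or EEG effect size, so there is nothing to reproduce. The check is a comparison of sections, followed by one illustration.

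**1. What does the number identify?** Two readings are possible.

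- *Subject-level code.* Section 10.1 applies the subject's study ID to all research material, and Section 11.2 gives the corresponding number a confidentiality purpose. On this reading all of a subject's tracings share one code, and the code does not mask the visit.
- *Per-recording code.* Section 6.3.12 assigns the number to the tracings and states a blinding purpose. Its next paragraph uses the word study for a single recording: "The study will be pruned so that only awake portions are present before the analyses begin". On this reading the code may mask the visit, provided that the file carries no date or visit label. That condition is not stated.

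**2. Does a per-recording code mask oil state within a stay?** Section 6.2.2.1 places the first dose on the morning of Visit 1 Day 2, within a 24-hour stay on continuous EEG, and keeps the EEG running for 4–6 hours after it. Section 6.2.3 has the Visit 2 stay capture several fasting and oil states, with a final dose on Day 2. Section 6.3.12, by contrast, describes 8-hour daytime recordings pruned to awake time. The document does not say whether one transmitted file spans pre-dose and post-dose hours, or whether clock time and dose marks reach the reader. Masking within the stay is therefore unspecified. The acute comparison needs it, because Sections 1.2 and 9.2.2.1 both state an effect over hours to days.

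**3. Where does judgement enter?** Rejection of detections feeds the generalized spike-wave rate. Confirmation of bursts feeds the count of discharges longer than 3 seconds. Choice of segment feeds the posterior dominant rhythm.

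**4. Illustration (assumed inputs, not in the document).** Suppose there is no true effect, and the reader rejects a fraction b of true detections before oil and a fraction t on oil. The apparent fall in rate is 1 − (1 − t)/(1 − b).

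| b (before oil) | t (on oil) | Apparent fall |
|---|---|---|
| 10% | 15% | 1 − 0.85/0.90 = 5.6% |
| 10% | 20% | 1 − 0.80/0.90 = 11.1% |
| 10% | 30% | 1 − 0.70/0.90 = 22.2% |
| 10% | 40% | 1 − 0.60/0.90 = 33.3% |

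If rejection does not differ by oil state (t = b), the fall is zero. The table shows how differential rejection would pass into the result. It is not evidence that it would occur.

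**5. Could EEG affect the decision?** Under Section 9.3, an age group with 9 or more favorable outcomes in 13 passes the second-stage boundary. Nine of 13 is 69% and 10 of 13 is 77%, and both fall within the 51–79% range in which Section 9.1 brings in the other outcomes. The route is real, but EEG is then one consideration among several.

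**The case against.** The strongest reply is that the protocol states an intent to blind and omits only operational detail. The number is attached to tracings, so a per-recording code is a fair reading. For the baseline, 6-month and 9-month analysis in Section 9.5, such a code would address the main contrast, which is between visits. Detection is automated, and the reader screens it against set criteria (generalized; 3 Hz and longer than 3 seconds), which leaves less room for expectation than a global impression score. EEG is secondary.

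Much of this stands, and it rules out several stronger readings that a reader might infer:

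- *That the EEG reading is unblinded.* The document is silent on visit and oil state. Silence shows that masking is not assured, not that it is absent.
- *That the number is the subject's study ID and stays the same at each visit.* Sections 10.1 and 11.2 make a subject-level code plausible, but neither mentions the EEG number or says that a code is constant across visits.
- *That visit and oil state form the only comparison in the trial.* They do for the EEG treatment effect. The primary analysis tests an attention response proportion against 50%, and Section 9.5 also compares age groups.
- *That a bias of 11% or 22% is expected.* Those values follow only from assumed rejection rates.

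The reply does not settle the acute comparison. A per-recording code alone does not hide pre-dose from post-dose time if a recording spans the dose, and no text says that recordings are split or that timing is removed.

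**Conclusion.** The point holds in a limited form. The measures that Section 6.3.12 describes do not assure masking of the reader to visit and oil state. Under a subject-level code the number does not mask the visit. Under a per-recording code the visit may be masked, but oil state within the Visit 1 and Visit 2 stays remains unassured.

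The exposure is limited to reader decisions made after automated detection, on a secondary outcome that bears on go/no-go only in the intermediate range. Its size cannot be estimated from the document. The conclusion assumes that no separate reading manual supplies the missing steps; none is referred to in the text. This is a cheap improvement, not a flaw that undermines the trial.

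**What to change.** Replace the blinding sentence in Section 6.3.12 with a short paragraph that specifies the following:

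1. Each recording gets its own random code, unrelated to the subject's study ID. For the acute comparison, each pre-dose or post-dose segment gets its own code.
2. Date, clock time, visit label and dose or meal annotations are removed before transmission.
3. The same central reader reads all of a subject's recordings in random order across visits, after that subject's last visit.
4. Someone other than the reader holds the key until the counts are locked.
5. Real-time EEG review for safety stays separate and unmasked.

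No extra reader or recording is needed, and Section 6.3.12 already has recordings held in local storage ahead of central review. The costs are data-handling time and later EEG results. A person who knows the dose times must do the segmenting, and the protocol should name that role, since Section 10.2 says only that the institution's CTSA division builds and maintains the database. Segment boundaries should be placed so that they do not cut through a discharge.

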6.3.13. Triheptanoin Initiation

Triheptanoin initiation will be accomplished in the Epilepsy Monitoring Unit located in the Children's Medical Center. Initiation will be completed under the supervision of [name] or one of the physician investigators.

6.3.14. Adherence Assessments

Adherence will be evaluated during a monthly phone call. Parents will be asked to rate adherence on a scale of 1 to 10. Quantity of oil remaining will also be assessed via the phone call.

7. MANAGEMENT OF ADVERSE EXPERIENCES

Previous experience with C7 oil in different populations has yielded no serious adverse effects. Due to the limited nature of the use of C7 oil, there are no definitive data available on how frequent the following side effects occur.

Diarrhea: Subjects who experience diarrhea may be instructed to increase the amount of fiber consumed with each meal. In addition, C7 will be administered in a fat free, sugar free food item, such as yogurt or pudding, and subjects are instructed to consume this food over 30 minutes in order to minimize diarrhea. Subjects who cannot tolerate the maximum tolerable dose will be discontinued from the study.

Stomach pain: Subjects who experience stomach pain at treatment initiation may, at the direction of [name] or M.D. co-investigator, reduce the dose of C7 oil to 50% for 2 days, then increase the daily dose back to the recommended level within a week. If subjects cannot tolerate the recommended dose, they will be discontinued from the study.

Weight gain: Subjects who experience weight gain (defined as any weight gain greater than 5% of the total body weight expected if the individual percentile were followed in the standard weight growth curve; CDC Standard Growth Curves, 2001) will be re-c counseled about the dietary changes recommended while taking the C7 oil supplement. Subjects will have a dietitian consult prior to treatment initiation and during treatment initiation, to discuss these changes (primarily reduction in other dietary fat). If subjects continue to experience weight gain, they will undergo a dietary assessment. If subjects have made recommended changes and continue to gain weight, they will be removed from the study and an adverse event will be reported.

8. CRITERIA FOR INTERVENTION DISCONTINUATION

Triheptanoin supplementation will be discontinued if any of the following occur:

- Any of the cited or other adverse experiences become intolerable to the subject
- Metabolic syndrome develops as assessed by glucose and lipid profiles
- Any elevation above laboratory normal range in hepatic transaminases or creatinine is noted
- Any clinically relevant blood cell count abnormality develops
- Non-compliance occurs
- Severe intercurrent illnesses take place

Subjects who discontinue due to the above reasons will be asked to return for a final research visit to complete exit procedures and receive referrals for ongoing care if necessary. Subjects who are discontinued due to adverse events will be followed via daily, alternate-day or weekly phone calls to assess resolution of the adverse event.

9. STATISTICAL CONSIDERATIONS

9.1. General Design Issues

In the proposed single-arm phase II trial, we define favorable impact on the neurocognitive outcome as at least 0.5 standard deviation (SD) improvement in performance on attention measures (measured as described above) after administration of C7. That is, impact on the outcome is determined by whether a treatment causes at least 0.5 SD improvement on the primary attention measure for that age group in a single arm trial and the interest is **primarily focused on reaching a decision on whether to progress with C7 to a future larger trial**. (Note: The SD is a normative parameter provided with the testing instruments). The evidence to make this decision is evaluated by testing the null hypothesis that the true efficacy rate is less than or equal to some pre-specified value. It is desirable to achieve this goal whilst minimizing the number of subjects exposed to a novel agent. Here, we use the Simon's optimal two-stage design that yields the smallest expected sample size when the null hypothesis is true.

We apply Simon's optimal two-stage design (24) using as primary outcome attention performance for each of three age groups. At least 0.5 SD improvement in performance on the primary attention measure after the administration of C7 is considered a favorable outcome. The measurement of 0.5 SD improvement is commonly accepted as the cutoff for a minimally clinically important difference, as described in various studies (e.g., 32, 33).

This protocol will yield data that allow a clear **go/ no-go decision** regarding whether C7 should proceed to an efficacy trial:

- If a favorable outcome occurs in less than 50% of subjects, we will recommend that C7 not proceed to an efficacy trial.
- If a favorable outcome occurs in at least 80% of subjects, we will recommend that C7 proceed to an efficacy trial.

The sample size estimation for this optimal two-stage design is given in Section 9.3.

If an intermediate number of subjects (51 – 79%) exhibit a favorable primary attention outcome, the rest of outcomes, including the long-term, 6-month responses, will be considered for the go/ no-go decision on the basis of impact on these outcomes and the disease process, in addition to tolerability and safety indicators.

Clinical significance and meaningfulness of the primary neurocognitive (attention) outcome: Attention is a core cognitive function that permits access to other areas of cognition and is commonly impaired in association with seizure disorders. Existing research has indicated that dietary interventions have the potential to promote attention functioning in children with G1D (26, 27). With regard to long-term outcomes, research in the field of childhood absence epilepsy has shown that even after attaining seizure freedom, attention deficits may remain (28). In other words, even normal EEG findings may not correspond to functional neuropsychological improvements. These findings in the field of childhood absence epilepsy are significant for the present study given that EEG seizures are more common than observable seizures in children with G1D. Additionally, these findings with regard to childhood absence epilepsy may help explain why language functioning improvements in children with G1D after administration of triheptanoin were not statistically significant in a previous trial (1). Again, attention is a core cognitive function that permits access to other areas of cognition (including language) and is commonly impaired in association with seizure disorders. For all of these reasons, attention functioning as measured by neuropsychological testing (described below in 6.3.9) may be a more relevant primary outcome for the present study than EEG findings. As noted above, the measurement of 0.5 SD improvement is commonly accepted as the cutoff for a minimally clinically important difference, as described in various studies (e.g., 32, 33), and thus in the present study we will look for this degree of improvement in performance on the primary measure of attention to answer the go/no-go decision for each age group.

Clinical significance and meaningfulness of the secondary EEG outcome: A specific (but variable across studies) percentage in EEG seizure reduction is a generally accepted outcome in epilepsy trials. The spike-wave and other EEG changes investigated above in this trial have the potential to reflect a meaningful disease burden reduction to patients that would be associated, if realized, with considerably fewer observable seizures, since EEG seizures are significantly more frequent than overt seizures in G1D (1). In this publication (1) we observed that, on average, a reduction in seizure rate comparable to the reduction sought above is associated with a significant acute (hours to days) impact on neuropsychological performance as well as sustained (months) quality of life and neuropsychological scores (1). As described in the proposal, this rate allowed many patients to significantly increase school performance, social interactions, autonomy and a decrease in or a cessation of antiseizure drugs. Every patient who participated in (1) experienced improvement in terms of one or more of these aspects and most improved in all of them. Thus, the expected reduction in EEG spike-wave burden after C7 treatment may be highly medically significant, but the definitive implications of this will be established only in more advance-phase trials. Therefore, we will attempt to relate attention scores (primary outcome) with EEG recordings (used here as a surrogate marker of the disease and a secondary outcome) to seek such correlations. The long-term aspects of the treatment, which may be expected to illustrate sustained or additional benefits as in (1) are also captured on the 6-month on-treatment study design.

Although a variety of designs were considered, including crossover designs for non-ketogenic diet subjects and randomization to C7 or ketogenic diet, several factors contributed to the development of an open-label design. The G1D population, while hypothesized to be greater than previously realized, is currently a relatively small population and the number of patients needed to adequately power a cross over study could be difficult to recruit. This holds true for a head to head comparison of C7 and ketogenic diet, although the increasing availability of genomic testing may increase the available population in the next few years. Finally, and most importantly, the safety and tolerability of C7 has not been rigorously proven in G1D. Therefore, this issue needs to be addressed before entering into advanced clinical trials.

A six-month, on-supplement follow up time period was chosen in order to provide long-term safety and tolerability data for triheptanoin. Additionally, we consulted with [name] (co-investigator), an established pediatric neuropsychologist expert in G1D. It is general practice to wait a minimum of 6 months after ischemic insult to the brain (such as traumatic brain injury or stroke) before assessing neurocognitive changes. This time period is consistent with how long it takes the brain to demonstrate performance improvement after these insults. Because chronic seizures can also induce long-term brain changes, 6 months was chosen to allow sufficient time for the brain to exhibit improvement that could be captured by the outcome measure tools.

The three-month exit visit allows us to assess whether changes in brain wave activity and other neurocognitive measures persist after withdrawal of oil.

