The Conners' Kiddie Continuous Performance Test- 2nd Edition (Conners K-CPT 2) is a norm-referenced, computerized measure of sustained attention and impulsivity that has normative data for children ages 4 years through 7 years. The K-CPT 2 uses pictures of objects rather than letters, which are used in the Conners CPT-3. The child is asked to respond to targets (all objects except soccer ball) and refrain from responding to non-targets (soccer ball) that appear on the computer screen. The median split -half reliability estimate across all scores was equal to .87. The median test-retest correlation was .57. These results suggest a good level of test-retest reliability.

The Conner's Continuous Performance Test- 3rd Edition (Conners CPT-3) is a norm-referenced, computerized measure of sustained attention and impulsivity that has normative data for children and adults ages 6 years and older. The CPT-3 requires subjects to press the space bar whenever any letter except the letter 'X' appears on the computer screen. Split-half reliability estimates of the Conners CPT-3 scales were calculated for the normative samples. Results were very strong – across all scores, the median split-half reliability estimate was .92.

The Peabody Picture Vocabulary Test-Fourth Edition (PPVT-4) is a norm-referenced measure of receptive vocabulary that has normative data for ages 2 years 6 months through age 90 years. The PPVT-4 has equivalent Forms A and B, and the PPVT-4 was co-normed with the Expressive Vocabulary Test-2 (EVT-2). For each item, the examiner says a word, and the examinee responds by selecting the picture that best illustrates that word's meaning. Alternate form mean reliability across ages is strong ($M=.89$), as is test-retest reliability across ages ($M=.93$). In addition to measuring receptive vocabulary, the PPVT-4 has demonstrated utility as a method for estimating premorbid intelligence (25), which represents an additional rationale for its inclusion in the present study. However, it should be noted that all subjects will participate in neuropsychological testing within the study protocol prior to administration of oil, thus providing baseline/pre-treatment data regarding neuropsychological functioning. It is not possible to obtain truly "premorbidity" neuropsychological data in the case of genetic disorders present at birth.

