9.2. Outcomes

9.2.1. Primary outcome

9.2.1.1. Attention performance

C7 provides a spectrum of short-term (hours to days) and long-term (over 6 months) benefits in subjects with G1D as measured by a 0.5 SD improvement in performance on the primary attention measure both in the acute and long-term.

Subjects receiving C7 supplementation will experience a significant (0.5 SD) improvement in performance on the primary attention measure for each subject's age group.

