9.3. Sample Size and Accrual

We estimated the sample size using the primary outcome (attention) for each of three age groups. The same method will be applied for sample size estimation in each of three age groups. An improvement of 0.5 SD or more on the primary attention measure

after the administration of C7 is considered a favorable outcome. This study will yield data that allow a clear go/no-go decision regarding whether C7 should proceed to an efficacy trial: If a favorable outcome occurs in less than 50% of subjects, we will recommend that C7 not proceed to an efficacy trial. If a favorable outcome occurs in at least 80% of subjects, we will recommend that C7 proceed to an efficacy trial.

The sample size was estimated using Simon's optimal two-stage design (24). The null hypothesis that the proportion of favorable outcome is 50% will be tested against a one-sided alternative hypothesis that the proportion of favorable outcome is 80%. In the first stage, 7 subjects will be accrued. If there are 4 or fewer favorable outcomes in these 7 subjects, the study will be stopped, and we will recommend that C7 not proceed to an efficacy trial. Otherwise, 6 additional subjects will be accrued for a total of 13 subjects. If 8 or fewer favorable outcomes are observed in 13 subjects by the end of stage two, then no further investigation of C7 is warranted. This design yields a type I error rate of 0.1 and power of 80% when the true favorable outcome occurs in 80% of subjects. We plan to recruit 15 subjects with an expected 15% dropout rate resulting in 13 subjects for each age group. That is, we will recruit a total of 45 subjects for this protocol.

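### The same 0.5 SD is both the improvement sought and the individual responder cut-off, so on a group-mean reading a treatment with exactly that effect sits at the 50% null

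*Combined protocol and SAP*

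**What the plan says.** Section 9.1 sets the favorable outcome at "at least 0.5 standard deviation (SD) improvement in performance on attention measures" and adds that "The SD is a normative parameter provided with the testing instruments", so the unit is the test's population SD and not the SD of change. Sections 9.1 and 9.3 apply this to each subject: "An improvement of 0.5 SD or more on the primary attention measure" counts as favorable. Section 9.1 justifies the value as the usual threshold for a minimally important difference.

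Section 9.2.1.1 uses the same size for the expected benefit: "Subjects receiving C7 supplementation will experience a significant (0.5 SD) improvement in performance on the primary attention measure".

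Section 9.3 turns this into a Simon optimal two-stage test in each of three age groups: "The null hypothesis that the proportion of favorable outcome is 50% will be tested against a one-sided alternative hypothesis" of 80%. A group stops at 4 or fewer favorable outcomes in 7. Otherwise it continues to 13 and fails at 8 or fewer. The stated type I error is 0.1 and the stated power 80%.

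Section 9.1 gives the decision rule differently: no-go below 50%, go at 80% or more, and for 51–79% the remaining outcomes are weighed.

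In Section 9.5 the primary analysis is the proportion of favorable outcomes with an exact interval, plus a comparison across age groups. The GEE for neuropsychological measures is assigned to the other measures. Attention scores enter a separate GEE on their correlation with EEG findings. No estimate of mean attention change is named, and none has a role in the decision.

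**The concern.** A cut-off for individuals and an effect for a group are different quantities. When both are set at 0.5 SD, a treatment whose average effect equals the stated important difference produces responders in only about half the subjects, and half is the rate the trial treats as not worth pursuing. The 80% alternative must then correspond to a larger average gain, and the plan does not say how large. At stake is a go/no-go decision in a rare disease: a group could be closed after 7 subjects although its average gain matched the difference the plan calls important, and no pre-specified estimate of that gain would be on the table.

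**Working it through.** **1. The plan's own figure.** Inputs from Section 9.3: n1 = 7, stop at ≤4; n = 13, fail at ≤8.

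P(go | p) = Σ over x = 5, 6, 7 of P(X1 = x; 7, p) × P(X2 ≥ 9 − x; 6, p)

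- p = 0.50: 0.1641 × 0.3438 + 0.0547 × 0.6563 + 0.0078 × 0.8906 = 0.0564 + 0.0359 + 0.0070 = 0.0992
- p = 0.80: 0.2753 × 0.9011 + 0.3670 × 0.9830 + 0.2097 × 0.9984 = 0.2480 + 0.3608 + 0.2094 = 0.8182

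The stated error rate of 0.1 and power of 80% reproduce. A full search also returns 4/7, 8/13 as the optimal design for these rates.

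**2. A mean effect of exactly 0.5 SD.** If changes are symmetric about a mean of 0.5 SD, P(change ≥ 0.5 SD) = 0.50, whatever the spread. Under the Section 9.3 rule, per age group:

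- stop at stage 1: P(X1 ≤ 4; 7, 0.5) = 0.773
- go: 0.099; no-go: 0.901

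If symmetry fails, no-go is 94.9% at a 45% responder rate, 82.6% at 55% and 72.4% at 60%.

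**3. The same case if the Section 9.1 band governs.** With the Section 9.3 sampling scheme kept, these results at p = 0.50 are no-go in 9.3 but intermediate in 9.1:

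- 4/7 (57%): 0.273
- 7/13 or 8/13 (54%, 62%): 0.0437 + 0.0648 = 0.109

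Automatic no-go is then only ≤3/7 (0.500) plus 5/13 or 6/13 (0.0026 + 0.0162 = 0.019), so 0.519, about 52%.

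**4. What 80% responders implies.** The documents give no SD of change. Assume normal change, with SD of change = √(2(1 − r)) in normative units, where r is the test-retest correlation. Then the mean needed = 0.5 + 0.842 × SD of change.

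| r | Source (Section 6.3.9) | SD of change | Mean for 80% |
|---|---|---|---|
| .87 | WPPSI-IV WMI stability | 0.510 | 0.93 |
| .82 | WISC-V WMI stability | 0.600 | 1.00 |
| .57 | K-CPT 2 median | 0.927 | 1.28 |

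The first two rows fit the youngest group (2 to 6 years), whose primary measure is the WMI: WPPSI-IV below 6 years and WISC-V from 6. The third is an illustration only. Section 6.3.9 says of the K-CPT 2: "The median test-retest correlation was .57". The testing schedule gives that test at 4–5 years, while the groups with a CPT primary measure are 7–11 and 12–35 years and take the CPT-3. No test-retest value is given for the CPT-3, so for those groups 0.93–1.28 SD (r = .87 to .57) is an assumed range.

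**5. What a mean-change estimate could show.** One-sided paired t-test at 0.10, true mean 0.5 SD, noncentral t with n − 1 degrees of freedom:

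| n | r = .57 | r = .87 |
|---|---|---|
| 13 | 72% | 98% |
| 7 | 52% | 87% |

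In the scenario of step 2, 77% of groups stop at 7, so the second row is the more relevant one.

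**The case against.** The plan's formal alternative is explicit, 80% favorable, and the design has 82% power for it. Section 9.2.1.1 does not use the word mean and can be read as restating the subject-level criterion. A reader might infer that the trial has about 10% power for its own hypothesis. The documents do not establish that: it needs the group-mean reading plus a symmetry assumption found nowhere in them. This objection stands as a limit on the claim.

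A reader might also infer that such a treatment is simply rejected 90% of the time. That holds under Section 9.3, but Section 9.1 has an intermediate band, and the text does not settle which governs.

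Nor does Section 9.5 analyze attention only as a proportion: scores enter the EEG-correlation GEE, and the closing paragraph on repeated measures does not exclude attention. What is missing is a named estimate of mean attention change with a role in the decision.

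Finally, requiring most subjects to pass a threshold is a legitimate, stricter screen. A mean change tested against zero is a weaker hurdle and, without a control arm, would count practice effects as benefit. That is a good reason to keep the responder rule. It does not remove the need to say how demanding the rule is.

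**Conclusion.** The point holds in a limited form. The plan uses 0.5 normative SD in two roles without connecting them. On the group-mean reading with symmetric change, the stated important difference coincides with the null: 9.9% go and 77% early stopping per age group under Section 9.3, or about 52% automatic no-go if the Section 9.1 band prevails. The two-stage design itself is sound for the responder rates it names.

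The undisclosed consequence is that 80% responders means an average gain of about twice the stated important difference, 0.93–1.0 SD, for the youngest group. This assumes normal change and that normative-sample stability and spread carry over to these patients across the study interval, which the documents do not show. For the two older groups no figure can be derived from the documents.

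**What to change.** 1. **Section 9.5:** add, as a supportive analysis, the pre-specified mean change from baseline in the normed primary attention score, with a confidence interval, per age group. Name it in Section 9.1 among the items weighed in the intermediate zone.
2. **Sections 9.1 and 9.3:** reconcile the decision rules. Results of 4/7 and 7–8/13 are no-go in one and intermediate in the other. Until this is settled, the added estimate cannot inform those results.
3. **Section 9.3:** say that the 80% power refers to an 80% responder rate, and give the implied mean gain with its assumptions. For the CPT-3 groups, mark it as an assumption and show the range.

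The responder rule, visits and sample size are unchanged. The cost is one more analysis and a less favorable statement of the detectable effect. The mean change is uncontrolled, cannot separate practice effects from treatment, and is imprecise in a group that stops at 7, so it should be labeled supportive.
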